### **17.1.1. ALL TEAES AND POST-TREATMENT AEs**

Number and percentage of subjects with at least one TEAE will be presented by SOC and PT. Should a subject experience multiple events within a SOC or PT, the subject will be counted only once for that SOC or PT. Subjects with at least one post-treatment AE will be summarized similarly.

Number and percentage of subjects with at least one TEAE will be broken down further by maximum severity. Subjects with at least one post-treatment AE will be summarized similarly.

#### **17.1.1.1. CTCAE Grading for AEs**

Severity will be classified according to the Common Terminology Criteria for AEs (CTCAE), version 4.03. TEAEs or post-treatment AEs starting after the first injection of study drug with a missing CTCAE grade will be classified as grade 3. Should a subject experience multiple events within a SOC or PT, only the subject's worst CTCAE grade will be counted for that SOC or PT.

#### **17.1.1.2. Relationship to Study Drug**

Relationship to study drug, as indicated by the Investigator, will be classified as unrelated, unlikely related, possibly related, probably related, or definitely related (increasing severity of relationship). A summary of TEAEs related to

Author:	[name]	Version Number:	2.0
Template No.:	CS_TP_BS016 Revision 6	Version Date:	23Nov2022
Effective Date:	02Dec2019	Reference:	CS_WI_BS005

study drug by SOC and PT will be prepared. A sub-table of post-treatment AEs related to study by SOC and PT will also be prepared.

A “Related” AE is defined as a TEAE or a post-treatment AE with a relationship to study drug of possibly related, probably related, or definitely related, while a “Non-related” AE is defined as a TEAE or post-treatment AE with a relationship to study drug of unrelated or unlikely related. TEAEs or post-treatment AEs with a missing relationship to study drug will be regarded as related to study drug. Should a subject experience multiple events within a SOC or PT, only the subject’s worst relationship will be counted for that SOC or PT.

#### **17.1.2. AEs WITH AN OUTCOME OF DEATH**

AEs with an outcome of death are those events which are recorded as “Fatal” on the AE page of the eCRF.

#### **17.1.3. SERIOUS ADVERSE EVENTS**

Serious Adverse Events (SAEs) are those events recorded as “Serious” on the AE page of the eCRF. A summary of serious TEAEs by SOC and PT will be prepared. A sub-table of post-treatment serious AEs by SOC and PT will also be prepared. Should a subject experience multiple events within a SOC or PT, the subject will be counted only once for that SOC or PT.

A listing of all SAEs will be provided.

#### **17.1.4. AEs LEADING TO DISCONTINUATION OF STUDY DRUG**

TEAEs leading to permanent discontinuation of study drug are those events recorded as “Drug Permanently Discontinued” on the AE pages of the eCRF. A summary of TEAEs leading to permanent discontinuation of study drug by SOC and PT will be prepared. A sub-table of post-treatment AEs leading to discontinuation of study drug by SOC and PT will also be prepared.

A listing of all AEs leading to permanent discontinuation of study drug will be provided.

#### **17.1.5. SEVERE HYPOGLYCAEMIC ADVERSE EVENTS**

Severe hypoglycaemic adverse events will be the AEs coded to the “Hypoglycaemia” Preferred Term (PT). A listing of all severe hypoglycaemic events will be provided. A summary table of severe hypoglycaemic adverse events may be provided if needed.

Author:	[name]	Version Number:	2.0
Template No.:	CS_TP_BS016 Revision 6	Version Date:	23Nov2022
Effective Date:	02Dec2019	Reference:	CS_WI_BS005

### 17.1.6. LOCAL IV-SITE REACTIONS

Local IV-site reactions will be the AEs coded to the “Injection site reaction” MedDRA High Level Term (HLT). A listing of all IV-site reactions will be provided. A summary table of local IV-site reaction adverse events may be provided if needed.

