## 5.7 Study Endpoints

Consistent with the study objectives, the primary endpoints will focus on the safety and tolerability of AVT001 treatment versus placebo.

The primary endpoints are:

- (a) The incidence of treatment-emergent adverse events (TEAEs).
- (b) Changes from baseline in clinical laboratory parameters.
- (c) The incidence and severity of local IV-site reactions.
- (d) Changes from baseline in vital signs and electrocardiograms.
- (e) Incidence of severe hypoglycemic events.

Secondary objectives focus on the CD8+ T-cell regulatory system and therapeutic outcomes associated with T1D. These pharmacodynamic effects of AVT001 will be assessed in an exploratory manner.

Secondary endpoints will include:

- (a) Assessment of the HLA-E-restricted CD8+ T cell regulatory activity (“potency assay”)
- (b) Changes from baseline in the area under the curve (AUC) of the stimulated C-peptide levels over the first 4 hours of a mixed meal tolerance test (MMTT)
- (c) Changes from baseline in HbA1c
- (d) Change from baseline in total daily insulin dose
- (e) Changes from baseline in autoantibody levels

The primary time point for analysis is Month 5, at which point the primary assessment of the study objectives is performed.

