## 7 Description of Study Drug

A study drug handling manual and study drug administration manual (Manual of Operating Procedures, ie, MOP) describes study drug management in detail. The MOP includes procedures for collection, transport, processing, storage, preparation (for dosing), and administration of study medication, as well as details regarding how the blinding is to be maintained during the infusion process. The following sections provide an overview of the key elements of those activities, but the MOP should be referred to for details.

Drug name and active ingredients: The study drug represents an individualized preparation of autologous immature dendritic cells, derived by culture from the subject's adherent primary monocytes with GM-CSF and IL-4 for 6 days, and loaded passively with the synthetic oligopeptide from Hsp60sp.

Formulation of dosage: AVT001 will be cryopreserved in infusible cryomedia in infusion bags. Each infusion bag will contain between  $7 \times 10^6$  and  $10 \times 10^6$  cells, and each subject randomized to AVT001 will have 3 such bags manufactured for infusion. The cryopreserved cells will be manufactured at the Dana Farber Cancer Institute Cell Manipulation Core Facility (DFCI-CMCF) and will be transported to the investigational site for infusion.

Route of administration: The infusions will be administered intravenously.

Frequency of administration: Three (3) infusions will be administered 30 (+/- 7) days apart. While there is a 7-day window for the infusions, they should occur at least 21 days apart.

Table 2 provides a summary description of the drug products, including the dosage form, the unit dose, and a physical description of the products.

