Subjects will be observed for at least 2 hours post-end of each infusion. Safety and tolerability assessments will be performed during and following the infusion, including measurement of vital signs. Vital sign frequency peri-infusion is monitored per the site's standard of care and a recommendation for the minimal frequency is described in the MOP. Local tolerability at the infusion site (such as pain, swelling, tenderness, and erythema) will be assessed via adverse event reporting. Any adverse events or new concomitant medications will be recorded.

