### 10.3 Response to AVT001

The response to AVT001 would be to activate HLA-E restricted CD8+ T cells *in vivo*, which would in turn selectively down-regulate any anti-self responses to control autoimmune diseases. In pre-clinical animal toxicology studies, the data showed no adverse effect/reaction to the treatment. In general, DC-based therapies are considered safe and tolerable therapies, with less toxicity comparable to checkpoint inhibitors in use or in trial.

There might be infusion site reactions such as swelling and irritation after the treatment of AVT001. In addition, there may be risks/discomforts involved in this study that are not known at this time.

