**Table 3 Schedule of Events (Protocol AVT001-T1D-01)**

Study Period	Screen/Rand/Leuk		Double-Blind Study Period (Visits 3-7)					Open-Label Study Period (Visits 8-11)		
			Double-Blind Treatment Period			Safety Assessment		Long-Term Follow-Up Period		
Study Day	$\leq -90^2$	*	1 	30 $\pm$ 7	60 $\pm$ 7	90 $\pm$ 7	150 $\pm$ 7	270 $\pm$ 7	360 $\pm$ 7	540 $\pm$ 7, 720 $\pm$ 7 / Early Term
Study Month	-3	*	-	1	2	3	5	9	12	18, 24
Visit Name	1	2	3	4	5	6	7	8	9	10, 11
Informed Consent	X									
Vein Check	X									
Randomization		X								
Medical History 	X		X							
Physical Exam 	X		X	X	X	X	X	X	X	X
Insulin Usage			X	X	X	X	X	X	X	X
Vital Signs 	X		X	X	X	X	X	X	X	X
MMTT for C-peptide			X				X		X	X
Severe Hypoglycemic Events Assessment			X	X	X	X	X	X	X	X
HbA1c and Antibody Samples	X		X	X	X	X	X	X	X	X
Laboratory Studies 	X		X	X	X	X	X	X	X	X
ECGs	X					X				
Viral Studies 	X									
Urine Pregnancy test	X		X	X	X		X			X (Day 720 /ET only)
Local tolerability of infusion site			X	X	X	X				
Leukapheresis		X 								
Potency Assay 	X (BD)	X (AVT)				X (BD)	X (BD)	X (BD)	X (BD)	X (BD)
Study Drug Administration 			X	X	X					
Adverse Events						On-going				
Prior/Commeds	Prior Meds					Commeds				

2 Screening assessments may be performed at more than 1 visit, if needed, and must be completed prior to randomization

3 At Study Day 1, a review of Medical history, symptom-driven PE, and review of eligibility should be performed prior to treatment. Details are included in note 4.

4 Medical history including prior treatment, current medicines, and drug allergies

5 Physical exam including blood pressure, pulse, temperature, weight. Can be symptom-driven physical examinations, except at Screening, Month 5, and Month 12.

6 Vital sign frequency peri-infusion is determined by site's standard of care; recommended (minimal) guidelines are provided in the MOP

7 Specified at each study visit: generally includes CMP, CBC w diff, Urine MicroAlbumin panel, CrCl (calculated); eGFR (calculated at screening only for eligibility)

8 HIV-1, HIV-2, HCV serology and HBV surface antigen

9 Leukapheresis to be performed after randomization, with sufficient time for IP/placebo manufacture prior to end of window between Screening Visit (Visit 1) and first infusion (Visit 3). Initial manufacture of blinded IP is expected to take a minimum of 28 days.

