## 2. STUDY OBJECTIVES AND ENDPOINTS

### 2.1. PRIMARY OBJECTIVE AND ENDPOINTS

Objectives	Endpoints
To determine the safety and tolerability profile of three doses of AVT001 (as compared to placebo) in T1D subjects within-vitro -reversible defects in the CD8+ T cell regulatory system.	Incidence of treatment-emergent adverse events (TEAEs).  Clinically significant changes from baseline in clinical laboratory parameters.  Incidence and severity of local IV-site reactions.  Changes from baseline in vital signs and electrocardiograms.  Incidence of severe hypoglycaemic events.

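### The primary endpoint of local IV-site reactions is selected by one injection-site MedDRA group, while the protocol describes infusion-site reactions, so the endpoint's own output may omit them

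*Combined protocol and SAP*

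**What the plan says.** Protocol Amendment 3, section 5.7, names "The incidence and severity of local IV-site reactions" as a primary endpoint, and SAP v2.0 section 2.1 carries it over as "Incidence and severity of local IV-site reactions".

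The protocol describes the site of dosing in one way:

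- Section 7, on route: "The infusions will be administered intravenously".
- Section 8.3.1, and in the same terms sections 7.1 and 8.3.2: "Local tolerability at the infusion site (such as pain, swelling, tenderness, and erythema) will be assessed via adverse event reporting".
- Section 10.3, on expected risks: "There might be infusion site reactions such as swelling and irritation after the treatment of AVT001".
- Table 3 has a row headed "Local tolerability of infusion site", marked at Visits 3 to 6 (Day 1 to Day 90).

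SAP v2.0 section 17.1.6 then defines the endpoint for analysis: "Local IV-site reactions will be the AEs coded to the “Injection site reaction” MedDRA High Level Term (HLT". SAP v1.0 section 17.1.6 has the same rule. A listing is promised, and then: "A summary table of local IV-site reaction adverse events may be provided if needed". Section 17.1 fixes the dictionary as MedDRA version 22.0.

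**The concern.** The analysis selects on one term group, and that group's name differs from the words the protocol uses for the same events. Local tolerability has no described eCRF flag or separate form. It reaches the database only as an adverse event, in the site's wording, and is then coded. Whether a reaction counts toward this endpoint therefore depends on the verbatim term, the coder's choice and this filter.

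If infusion-site terms lie outside the named group, the output carrying the endpoint's name could be short of events, or empty, while the reactions that section 10.3 expects sit elsewhere in the safety tables. A reader judging local tolerability will go first to the output bearing that label.

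A second, smaller matter needs no dictionary. The endpoint is incidence and severity, but 17.1.6 commits only to a listing. By contrast, sections 17.1.3 and 17.1.4 commit to summaries of serious events and of events leading to discontinuation.

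**Working it through.** **1. Wording set side by side.**

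- Endpoint name (protocol 5.7, SAP 2.1): IV-site.
- Expected events and their capture (protocol 7.1, 8.3.1, 8.3.2, 10.3, Table 3): infusion site.
- Selection rule (SAP 17.1.6): injection site, one High Level Term.
- Bridge between the last two: none. No section adds an infusion-site term, and none tells sites or coders to treat infusion-site events as injection-site events.

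**2. What the documents cannot settle.** They give the MedDRA version but not its hierarchy. Whether infusion-site terms fall under another High Level Term has to be looked up. The wording mismatch is established; the loss of events is conditional on that lookup.

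**3. The plan's own figure.** SAP section 7.1 takes 14 AVT001 subjects and a true incidence of 12%, claims at least 80% power to observe at least one event, and extends the claim to local tolerability events.

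1 − (1 − 0.12)^14 = 1 − 0.88^14 = 0.833

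This agrees with the stated lower bound. It is the chance that at least one of 14 subjects has an event. Coding does not alter it, because the event is still recorded and tabulated.

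**4. What coding could alter.** The only quantity at risk is the chance that the IV-site output shows at least one subject. Let f be the share of affected subjects whose reactions code outside the named group. The documents give no value for f, so the full range is shown:

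1 − (1 − 0.12 × (1 − f))^14

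- f = 0: 0.833
- f = 0.10: 0.798
- f = 0.25: 0.733
- f = 0.50: 0.579
- f = 0.75: 0.347
- f = 1: 0

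The value reaches 80% when the effective incidence is 1 − 0.2^(1/14) = 0.1086, that is, f = 1 − 0.1086/0.12 = 0.095. These figures describe one output under assumed values of f. They do not estimate what will happen in this trial.

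**5. Where omitted events would still appear.** SAP 17.1 lists all adverse events, with relatedness and outcome. Section 17.1.1 tabulates treatment-emergent events by system organ class and preferred term, and by maximum severity, with the same for post-treatment events. Section 17 presents these summaries by treatment group.

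**The case against.** The strongest reply is that nothing is lost from the report. A differently coded reaction still appears by preferred term, by arm and by severity, in a trial of about 24 subjects with no safety testing. This stands, and it limits the harm to the output labelled as the endpoint.

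Second, the terminology is mixed. Protocol 7.1 calls the doses injections, SAP 6.1 dates the study from the first injection, and the output shells are a separate document. Some sites may therefore write injection-site terms. This also stands, but it makes capture unpredictable and does not close the gap.

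Third, with few events a listing may suffice, and 17.1.5 uses the same optional wording for severe hypoglycaemia. In addition, 17.1 promises an overall by-arm count of subjects for the categories in its subsections, which on a literal reading includes this one. That would supply incidence, although through the same filter and without grade. The table point is therefore modest.

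Two stronger readings are tempting. A reader might infer that the plan's power falls from 83% to 58%. It does not: 58% needs an assumed half of events to be coded elsewhere, and it concerns one output, not whether events occur. A reader might also infer that the trial will wrongly report clean local tolerability. That would require both an unfavourable dictionary grouping, which the documents do not show, and disregard of the main adverse event tables.

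**Conclusion.** The selection rule for a primary endpoint does not match the protocol's description of the events it is meant to count, and this can be seen from the documents alone. If infusion-site terms sit outside the named High Level Term in MedDRA 22.0, expected reactions would be missing from the IV-site listing, from the optional table, and from any row for this category in the overall summary. They would not be missing from the general adverse event outputs.

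The share missed cannot be estimated; 0 to 100% is the honest range. The 83% stated in step 3 is unaffected. The conclusion rests on two things: the absence of any text mapping infusion-site to injection-site coding, and a dictionary check still to be done. Because the stated rule can leave out the very events the protocol anticipates, this is more than a missing detail and is worth correcting.

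**What to change.** In SAP section 17.1.6:

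- Check the grouping in MedDRA 22.0, then define local IV-site reactions by a pre-specified term list covering infusion-site and injection-site reactions. Add catheter-site and puncture-site terms only where the verbatim places the event at the study-drug infusion site, so that blood-draw events are dropped.
- Have that verbatim check done by a reviewer masked to allocation. SAP 4.2 records unblinding on 17 May 2022, so the study team can no longer be assumed blind.
- Make the summary table mandatory: by arm, subjects with at least one reaction (n, %) and maximum CTCAE grade.
- Apply the definition to the Month 12 supplemental and Month 24 final analyses. SAP 4.4 already foresees an amendment before the final lock.
- Re-run it on the Month 5 data, since the scheduled local assessments end at Day 90, and label it as a post-unblinding change. Showing the result under the existing rule alongside would make any difference visible.

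The cost is a dictionary lookup, a short verbatim check and one small table. No new data are needed. If the existing rule missed nothing, the re-run will show that.

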## 17.2. DEATHS

A listing of all deaths will be provided.

## 17.3. LABORATORY EVALUATIONS

A urine pregnancy test will be performed at screening. Chemistry, hematology, and urinalysis (microalbumin panel) will be performed as per the schedule of events (refer to protocol, Table 3). A list of laboratory parameters to be included in the outputs is included in [APPENDIX 2](#).

Quantitative laboratory parameters reported as “< X”, i.e. below the lower limit of quantification (BLQ) or “> X”, i.e. above the upper limit of quantification (ULQ), will be converted to X for the purpose of quantitative summaries, but will be presented as recorded, i.e. as “< X” or “> X” in the listings.

The following summaries will be provided by treatment group based on the SAF analysis population for each chemistry, hematology, and urine microalbumin laboratory parameter:

- Observed and change from baseline in Standard International (SI) units by visit (for quantitative parameters)
- Shift from baseline to the worst post-baseline observed value according to the Common Terminology Criteria for Adverse Events (CTCAE) toxicity grades (for quantitative parameters with available CTCAE toxicity grades; refer to [Section 17.3.11](#))
- Shifts from baseline to the maximum/minimum post-baseline observed value according to normal range criteria (for quantitative parameters without CTCAE toxicity grades; refer to [Section 17.3.12](#))

All laboratory data will be listed.

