#### ***Safety Assessment***

Adverse events will be reported using the MedDRA coding dictionary. Tabulations will include an overall incidence of at least one adverse event, incidence within body system, and incidence by preferred term. Each subject may only contribute once (ie, first occurrence) to each of the incidence rates, regardless of the number of occurrences. The incidence of adverse events will be presented as follows:

- The incidence of treatment-emergent adverse events (TEAEs), ie, those events that start on or after the first dose of study medication, will be tabulated by treatment for the Treatment Phase. This will include events starting within 30 days following the last dose.
- The incidence of post-treatment events (those events that start more than 30 days following the last dose) will be tabulated.

Subjects with serious adverse events (including deaths) and subjects who discontinue due to adverse events will be listed. Subjects who have other significant serious adverse events deemed to be of special interest because of clinical importance will also be listed.

Laboratory, vital signs, and ECG outcomes will be assessed for changes over time as well as clinically significant shifts from pre-treatment. The incidence of severe hypoglycemic events will be tabulated.

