## 5.4 Study Duration

There are three pre-defined periods in this study.

- Screening and cell collection period will last up to 3 months
- Treatment period will consist of 3 doses, ~30 days apart (Baseline, Month 1, Month 2) and a 1-month post-last dose assessment period (through Month 3). Thus, the treatment period is defined to be 3 months in duration.
- Post-Treatment Follow-up Period will extend 21 additional months (and thus through Month 24 of the study).

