## 9.7 Clinical Laboratories, ECGs, and Vital Signs

Descriptive statistics at Baseline, on-treatment, and change from Baseline will be calculated for the subjects who have both Baseline and on-treatment evaluations. Shifts from Baseline to on-treatment will be examined. Potentially clinically significant laboratory values will be identified and listed.

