## 4. PLANNED ANALYSES

The following analyses will be performed for this study:

- Primary analysis after the last subject completes the Month 5 study visit (after study unblinding). All available data will be analyzed.
- Supplemental analysis after the last subject completes the Month 12 study visit (Day 360).

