## 17.4. VITAL SIGNS

The following vital sign parameters will be collected for this study as per the schedule of events (refer to protocol, Table 3):

- Systolic blood pressure (SBP) (mmHg)
- Diastolic blood pressure (DBP) (mmHg)
- Pulse rate (beats per minute [bpm])
- Oxygen saturation (%)
- Body temperature (°C)

Author:	[name]	Version Number:	2.0
Template No.:	CS_TP_BS016 Revision 6	Version Date:	23Nov2022
Effective Date:	02Dec2019	Reference:	CS_WI_BS005

- Weight (kg)

The following summaries will be provided by treatment group based on the SAF analysis population for each vital sign parameter:

- Observed and change from baseline by visit and timepoint
- Number and percentages of subjects with at least one markedly abnormal post-baseline observed value/change from baseline (refer to [Section 17.4.1](#))

All vital sign data will be listed. Vitals signs meeting one of the markedly abnormal criteria in Section 17.4.1 will be identified.

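### SAP v2.0 17.3 and 17.4 count laboratory shifts and vital-sign flags over all post-baseline follow-up, where protocol 9.7 calls for on-treatment shifts, and SAP 3.3 does not declare the difference

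*Combined protocol and SAP*

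**What the plan says.** Protocol 9.7 covers laboratories, ECGs and vital signs together. It states "Shifts from Baseline to on-treatment will be examined", and its summary rule is "Descriptive statistics at Baseline, on-treatment, and change from Baseline will be calculated for the subjects who have both Baseline and on-treatment evaluations". Protocol 5.4 runs the treatment period through Month 3: "Thus, the treatment period is defined to be 3 months in duration".

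SAP v2.0 sets different rules:

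- 17.3, parameters with toxicity grades: "Shift from baseline to the worst post-baseline observed value according to the Common Terminology Criteria for Adverse Events (CTCAE) toxicity grades".
- 17.3, other quantitative parameters: "Shifts from baseline to the maximum/minimum post-baseline observed value according to normal range criteria".
- 17.4, vital signs: "Number and percentages of subjects with at least one markedly abnormal post-baseline observed value/change from baseline".

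None of these has an end date, and no other section supplies one. For the primary analysis, section 4 says "All available data will be analyzed". Section 6.4 applies no visit windows. Section 6.3 lets unscheduled, retest and early-termination values feed shift tables. Section 3.3, the list of changes from the protocol, covers only the potency assay and the Day 360 analysis. SAP v1.0 has the same rules in its 17.3 and 17.4.

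Adverse events are handled differently. SAP 17.1 splits them at 30 days after the last dose and gives each summary table a treatment-emergent and a post-treatment part.

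**The concern.** Changes in laboratory parameters and in vital signs are primary endpoints (b) and (d). A reader of the protocol would expect the shift tables to show what happened during treatment. Under the SAP, a Day 720 laboratory value, taken 720 − 60 = 660 days after the last scheduled infusion, counts the same as one taken between infusions.

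Two consequences follow. The percentage of subjects with a worst-case shift rises with the number of visits they have had, so it depends partly on when they enrolled. An excess confined to the treatment period is also harder to see once later background abnormalities are added to both arms. With about 16 and 8 subjects and no safety testing planned, these counts will be read directly.

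**Working it through.** **The plan's own safety figure.** With 14 subjects and a true incidence of 12%, the chance of at least one event is 1 − 0.88^14 = 0.833, which agrees with the stated 80% or more. The enlargement also agrees: 21 / 0.90 = 23.3, rounded up to 24. The present point does not depend on either figure.

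**Scheduled visits.** Protocol Table 3 places post-baseline laboratory and vital-sign visits on Days 30, 60, 90, 150, 270, 360, 540 and 720. Three are within the treatment period and five after it. The cumulative count is 4 by Day 150, 6 by Day 360, 7 by Day 540 and 8 by Day 720.

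**Follow-up at the primary lock.** Protocol 5.5 doses the first six subjects in sequence, each after the previous subject's Month 1 visit. That visit can fall as early as Day 23, so each gap is at least 22 days. Protocol 4.7 says the DSMB had reviewed all six when Amendment 3 was written (01Feb2021). Five gaps between subjects plus one month for the sixth give 6 × 22 = 132 days, so the first dose was no later than about 22Sep2020. From 01Feb2021 to the lock on 29APR2022 is 452 days. The first subject was therefore at Day 132 + 452 + 1 = 585 or later, with 7 visits due if still followed. The last subject needed only 4. An eighth visit would have been due only for a first dose about 719 days before the lock (around 10May2020) or earlier, which the documents neither show nor exclude.

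By the SAP v2.0 sign-off on 06Dec2022 the first subject was past Day 800. All 8 visits were due for that subject at the Month 12 analysis, against 6 for a subject just reaching Day 360.

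**Chance of an incidental abnormality.** The per-visit background rate p is an assumption; the documents give none. With independent visits, the chance of at least one in k visits is 1 − (1 − p)^k.

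| p | 3 visits | 4 | 6 | 7 | 8 |
|---|---|---|---|---|---|
| 1% | 3.0% | 3.9% | 5.9% | 6.8% | 7.7% |
| 2.5% | 7.3% | 9.6% | 14.1% | 16.2% | 18.3% |
| 5% | 14.3% | 18.5% | 26.5% | 30.2% | 33.7% |
| 10% | 27.1% | 34.4% | 46.9% | 52.2% | 57.0% |

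At 5% in 16 AVT001 subjects, that is 2.3 subjects expected over 3 visits and 5.4 over 8.

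**Dilution.** Also assume a 10-point per-visit excess on AVT001 at the three treatment-period visits only. The arm difference after k visits is (1 − p)^(k−3) × [(1 − p)^3 − (0.90 − p)^3]. At p = 5% the bracket is 0.8574 − 0.6141 = 0.243.

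| p | 3 visits | 4 | 7 | Loss at 4 to 7 visits |
|---|---|---|---|---|
| 1% | 26.5 | 26.3 | 25.5 | 0.3 to 1.0 points |
| 5% | 24.3 | 23.1 | 19.8 | 1.2 to 4.5 points |
| 10% | 21.7 | 19.5 | 14.2 | 2.2 to 7.5 points |

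With all 8 visits at p = 5% the difference is 18.8 points, but that does not describe the Month 5 lock.

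**The case against.** **By-visit summaries remain.** 17.3 and 17.4 keep observed values and changes by visit, all data are listed, and markedly abnormal vital signs are identified. A reader might infer that the on-treatment analysis has been removed altogether; it has not. What is missing is the number of subjects who shifted during treatment. By-visit tables do not give that, and they leave out unscheduled and early-termination values.

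**The protocol is not uniform.** Its synopsis says "Laboratory, vital signs, and ECG outcomes will be assessed for changes over time as well as clinically significant shifts from pre-treatment" and names no period. Section 9.7 does not define on-treatment, so ending it at Day 90 is an inference from 5.4. Both points are fair, but the synopsis is silent rather than contrary and 9.7 is the more specific text. The Day 90 limit also fits the adverse event rule for a subject dosed on schedule (60 + 30 = 90).

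**Month 5 is the primary time point.** Protocol 8.4.1 makes Day 150 a full safety assessment, and a treatment-period table leaves it out. Keeping an all-follow-up table as a supplement answers this.

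**The visit count suits laboratories better than vital signs.** Vital signs are also monitored during each infusion and for two hours afterwards, so the treatment period holds more than three of their measurement occasions. This stands, and the arithmetic above should be read for laboratories.

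**Randomisation.** A reader might infer that unequal follow-up biases the arm comparison. Follow-up differs between subjects, but blocked 2:1 allocation (protocol 8.2.2) keeps enrolment time roughly balanced between arms. Nothing in the documents shows a difference.

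**Timing.** The rule was in SAP v1.0, final on 28MAR2022, before unblinding on 17MAY2022, and the primary outputs were delivered on 10JUN2022. Recut Month 5 tables would be post-unblinding work and should be labelled so.

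**Conclusion.** The point holds for two sets of outputs: the laboratory shift tables in 17.3 and the markedly-abnormal vital-sign counts in 17.4. They depart from protocol 9.7, the departure is undeclared, and they pool the treatment period with later follow-up of unequal length.

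The size is modest at the Month 5 lock. With an assumed 5% background and a 10-point on-treatment excess, the arm difference falls by about 1 to 4.5 points; across backgrounds of 1% to 10% the range is 0.3 to 7.5. These figures assume independent visits and an excess confined to treatment. Positive correlation between a subject's visits would slow the growth with visit number.

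It would be too strong to say that the primary safety counts as a whole are affected. Treatment-emergent adverse events are already windowed, and ECGs have one scheduled post-baseline time, Day 90. Full Month 24 data were also not the basis of the Month 5 result: values that late belong mainly to the Month 12 lock for the earliest subjects and to the final analysis, which SAP 4.4 leaves to a further amendment.

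**What to change.** In 17.3 and 17.4, present each shift table and each markedly-abnormal count separately for two periods: from the first infusion through the Day 90 visit, including unscheduled values, and post-treatment follow-up. Show the number of subjects evaluated in each period. Label any all-follow-up version supplementary, and record the difference from protocol 9.7 in 3.3.

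Apply this to the Month 12 analysis and to the SAP amendment for Month 24, and add the split to the Month 5 report as a supplementary table. The adverse event tables need no Day 150 cut-off: they already separate the periods, and section 4 calls for all available data.

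The cost is SAP wording, programming and checking of a second set of tables, and a note that the Month 5 addition was made after unblinding. No new data are needed.
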